This study will test the efficacy of three formulations. Picaridin-based repellents have been marketed around the world for a decade, but the product is comparatively recent in the U.S. market, where Spectrum introduced it in 2005. The U.S. Centers for Disease Control has acknowledged the existence of substantial consumer interest in new and effective insect repellent products, and that Picaridin-based repellents are among the very few of sufficiently high efficacy to offer reliable personal protection against vectors of West Nile virus (in April 2005). However, few Picaridin products are currently marketed in the U.S., and comparatively little study has been made of its performance as a tick repellent in the U.S. Prevention of tick bites

and the reduction of the risks of contracting tick-borne diseases are of substantial interest to U.S. consumers and public health professionals. Thus, there is substantial merit in its further study and the development of new Picaridin-based repellent products toward unconditional registration by the U.S. EPA.

Information regarding the stability of the end products is available from the Sponsor in a separate study.

The main endpoint of this study will be the conclusion of a tick repellent efficacy test of Picaridin-based topical repellents in the laboratory, with the data set suitable for submission to U.S. EPA to comply with the conditions of registration, and including the bridging of performance data to related products. Initial dosage determination ('dosimetry') will also be conducted with 10 subjects per formulation, some of whom may then go on to participate in efficacy testing. Dosimetry will be conducted at the letterhead address. When 10 subjects have completed dosimetry for each formulation, the resulting data will be used to determine dosing for the efficacy testing.

5.3 Rationale for use of Human Subjects:

Human subjects are required because they represent the target system for the test material; sufficiently reliable replacement models for repellency testing do not exist. In addition, subjects will self-administer the test articles during dose determination. Ten subjects are required in order to reduce variation around the population means that we will describe.

5.4 Balance of Risks and Benefits:

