- 9.1.2.1 Known to be phobic of ticks.

- 9.1.2.2 Known to be sensitive or showing sensitivity to any of the test product ingredients after application.
- 9.1.2.3 Poor physical condition.
- 9.1.2.4 Unwilling to submit to brief query about personal condition.
- 9.1.2.5 Use of insect repellent within 1 day preceding the study.
- 9.1.2.6 Unwilling to refrain from use of perfumed products, alcoholic beverages or smoking after 9 p.m. the evening preceding the test and throughout the test.
- 9.1.2.7 Known to be pregnant or lactating. Pregnancy will be self-checked by each female volunteer on the morning of the repellent test using an OTC test kit provided by Carroll-Loye. Results of each such test will be immediately verified by direct inspection by a technician trained to make that assessment. Only volunteers scored as nonpregnant will be allowed to participate.
- 9.1.2.8 Unable to deliver the test materials or nymphal ticks to own left and right arms.
- 9.1.2.9 Unable to see nymphal ticks on skin or otherwise effectively monitor them on skin.
- 9.1.3.10 Student or employee of the Study Director.

9.1.3 Number of Subjects and Rationale for Sample Sizes:

In both dosimetry and efficacy testing, we will engage 10 subjects per treatment. Each subject is a replicate. It is possible that a single set of 10 individuals could complete all parts of the study. It is much more likely that substantially more than 10 individuals will participate.

The number of subjects is chosen as a compromise between several conflicting factors. In the absence of clear means of estimating the distribution of outcome values, it is difficult to predict an ideal sample size. From a strictly scientific standpoint, an appropriate response under such circumstances would be to increase the sample size, but ethical and economic considerations demand the opposite in

the present study, particularly during the efficacy testing phase.

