All such potential participants are screened or re-screened for suitability for each test in a private, one-on-one conversation with the Study Director. Some former subjects have been excluded from repellent testing, for example, because they surpassed the upper age limit when the health risks from vector-borne disease statistically more serious. The Exclusion Criteria (see §9.1.2, above) are exercised by asking each candidate to address them in the interview with the Study Director. It is explained to female candidates that pregnancy will be assessed directly on the test day. The Study Director encourages candidates to ask questions and ask for clarification at any time during the interview and in all activities that follow. To candidates who pass screening, the Study Director describes the test's purpose, as well as necessary procedures and expected comportment, in plain language (in English). Candidates are then asked if they would like to retire from consideration. If they wish to remain in consideration, it is emphasized that they may withdraw from the test at any time during the test without penalty to their compensation. This freedom is especially re-emphasized in cases in which considerable effort or expense has been required to include a subject (e.g., travel to a distant site), to discourage the conception that that effort or expense creates any added obligation in the subject.

Candidates are given copies of the State of California Department of Pesticide Regulation *Experimental Subject's Bill of Rights* (appended) to read in the presence of Carroll-Loye personnel. They are also given a copy of the IRB-approved consent form to read. The amount and form of compensation are described. They are again encouraged to ask any questions about the test, which may include understanding its purpose more fully, understanding risks and discomforts more fully, and understanding treatment and compensation for injury more fully. While the majority of our subjects have worked with us on an occasional basis for a number of years, we encourage them to seriously evaluate their interests and concerns about participation each time. We ask them not to sign on immediately, but to give the situation due consideration (normally at least one day, sometimes less for those who have participated in multiple

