prior studies). Because most of the volunteers are researchers and/or have advanced degrees in the life sciences, or work directly with or otherwise regularly encounter biting arthropods in infested habitats, we regard their motivations and decisions to participate as being well-considered and well-informed. Accordingly, we normally accept their decisions to participate if they so choose to following due consideration. Nonetheless, the Study Director retains the final right to refuse participation to any candidate.

9.1.6 Identification method and records retention:

Subjects will initially be identified by first and last name, and assigned a unique number for purposes of this study. Individual data will be entered into the computer for retention and analysis with reference to individual number, not name. Records relating individual names to individual numbers will be retained separately. The Study Director will retain records indefinitely. Subjects may obtain their own records from the Study Director.

9.1.7 Enrollment of alternate subjects and its relation to individual privacy:

We will enroll 3 more subjects than are required to meet our sample size. All subjects will be informed during the consent process that on the day of testing, a small number of subjects may be designated as alternates and sent away after being compensated for coming to the test site. Alternate subjects may return later to replace subjects that initiate testing but withdraw before useful data are generated. They also serve as insurance against any enrolled subjects who fail to appear.

The possibility that any subject may be designated as an alternate will assist in protecting the privacy of any subject that must withdraw in or near the presence of other subjects at the start of the test day (i.e., before treatment and testing begins), for reasons such as a positive pregnancy test result, or for any other personal circumstance.

9.2 Blinding of Study:

None

9.3. Study Material Administration:

Experienced personnel will administer Study Materials to each subject. Test products will be applied volumetrically to the skin surface from a small syringe, and spread on the site as evenly as possible with one fingertip in a surgical glove, using a light rubbing motion. Skin surfaces to be treated are first cleansed with water and a fragrance-free detergent soap, rinsed with a 35% ethanol-in-water solution, then towel-dried.

9.4 Subject Consent:

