Approximately two weeks to four days before repellent efficacy testing, subjects will be trained by technical personnel in handling and observing ticks. Subjects will learn how to manipulate ticks with fine paintbrushes, place them on their own forearms, observe and quantify tick movement on their arms, and dispose of used ticks. This training will be documented. This 'hands-on' experience will assist subjects in collecting data accurately and handling ticks safely during the repellent efficacy trial. It is detailed in a training document appended to this protocol.

10 TEST VARIABLES AND THEIR MEASUREMENT:

10.1 Variables to be Measured:

Subject forearm surface area.

Subject self-dosing behaviors.

Weight of test materials delivered to the surrogate skin (gauze) dosimeters.

Number of tick crossings on the treated surface of the skin.

10.2 When Variable will be Assessed:

Dosage will be calculated on the basis of surface area of the lower limb skin that is treated. Measurements to calculate that surface area will be made on each subject in advance of application of the test materials.

Self-dosing behavior (distance of spray nozzles from skin, number of pumps or sweeps of delivery apparatus) will be measured at least two days prior to Test Day 1.

Passive dosimeters (described in section 10.1.3) will be weighed before application of the test materials and again between one and five minutes after application of the test materials.

Subjects will record any Crossings as they occur. Data are recorded in three-minute exposures at 1- minute intervals. The time at which the application of a treatment is completed is recorded as t_0 ('time zero'). The first exposure begins approximately 15 minutes after treatment.

10.3 Procedures for Assessing Variable:

10.4.1 Limb dimensions and surface area:

The term 'limb' refers to the forearm. The surface area of each limb is computed as the average of 4 evenly spaced circumferences (2 peripheral, 2 central) of the forearm (elbow to wrist) multiplied by the length of treatment area.

10.3.2 Familiarization with, and subject use, of the spray apparatus:

Variable assessment will involve a 2-step process, namely subject familiarization with the spray apparatus, followed by dosage measurement.

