Put a new latex glove on each hand. Spray material onto one limb only. The technician will tell you to which limb to apply spray. You and the technician will collect the same data as previously.

After you have completed spraying, keep both limbs from making contact with any surface. All bracelets will be removed by a technician and taken for weighing.

Discard your gloves, and wash both limbs with cleanser and dry them thoroughly with a towel.

Repeat these procedures until you have made at total of three spray samples for the first limb, and three more for the second limb. If you have completed sampling on, e.g., both arms, the technician may then ask you to repeat the same measurement on both legs. Be sure to discard your gloves, and wash all limbs with cleanser and dry them thoroughly with a towel, including after the last application.”

1. Study subjects
e. Dosimetry (pump spray only)
i. practice
ii. performance
(v. 1, 16 January 2007)

Carroll-Loye Biological Research

[name]

[name]

[contact]

<http://www.carroll-loye.com/>

CLBR Training Manual

§1.b. Handling ticks and observing their movement on the skin

A. Goals of exercise

1. Learn to move and handle ticks using a fine artist's paintbrush in preparation for participate in a tick repellent study.
2. Learn to observe ticks and measure their movement in preparation for collecting data on the effectiveness of a repellent against ticks.

B. General information

1. A technician will show you how you how to remove ticks from a plastic vial using a small paintbrush, how to avoid injuring the ticks, and how to place them on you arm and remove them, and how to dispose of them.
2. A technician will draw three lines on your forearm, each 3 cm apart. You will practice placing ticks on the arm and both watching and timing their movement in relation to those lines.
3. You will work one tick at one time. The ticks are reared in the laboratory and are free from disease.

C. Materials and equipment needed

1. Fine paintbrush
2. Marking pen
3. Approximately 6 unfed ticks
4. Labeled vials for accessing and disposing of ticks
5. Shallow pans with water
6. Timer
7. Practice data sheet and pen

D. Learning the methods

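### The pregnancy kit test is set only for the morning of the repellent test, so dosimetry subjects contact product before it and dosimetry-only subjects are never tested

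*Protocol*

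**What the plan says.** Protocol §9.1.2.7 excludes known pregnancy and lactation and adds an objective check: "Pregnancy will be self-checked by each female volunteer on the morning of the repellent test using an OTC test kit". A trained technician verifies the result, and the section closes with a gate: "Only volunteers scored as nonpregnant will be allowed to participate".

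Two other sections give the same timing. In §9.1.5.3: "It is explained to female candidates that pregnancy will be assessed directly on the test day". In §9.1.7, alternates give privacy to someone who has to withdraw "at the start of the test day (i.e., before treatment and testing begins), for reasons such as a positive pregnancy test result".

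Dosimetry comes earlier. The schedule in §7.2 places it in days -30 to -2, and §10.2 says that self-dosing behavior "will be measured at least two days prior to Test Day 1". §8.1 states that every dosimetry subject is treated. §10.3.2 has subjects practise with the test material on their own limbs, and the pump-spray training manual then says: "Repeat these procedures until you have made at total of three spray samples for the first limb, and three more for the second limb". The two phases need not share subjects, since §5.2 plans dosimetry in "10 subjects per formulation, some of whom may then go on to participate in efficacy testing".

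Tick training also comes first, under §9.6: "Approximately two weeks to four days before repellent efficacy testing, subjects will be trained by technical personnel in handling and observing ticks".

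**The concern.** The gate in §9.1.2.7 is worded for participation in general, but the test that feeds it belongs to one phase. A woman in dosimetry puts product on her skin before any test. If she does not go on to efficacy testing, she has no repellent-test morning and so no test at all.

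The protocol evidently does not regard the interview as sufficient on its own, because it adds a kit and a technician's verification. It gives no reason why one phase with product on skin has that check and the other does not. §9.1.4 excludes pregnant women on general medical grounds and makes no exception for dosimetry. At stake is subject safety and the protocol's consistency with its own eligibility rule.

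**Working it through.** The protocol gives no figure to reproduce here. The check is a timeline and two counts.

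**Timeline relative to Test Day 1**

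| Event | Timing | Contact | Source |
|---|---|---|---|
| Screening interview | before any session | none | §9.1.5.3 |
| Dosimetry | days -30 to -2 | test material on forearms | §§7.2, 8.1, 10.2, 10.3.2 |
| Tick training | about 14 to 4 days before efficacy testing | live ticks, no repellent | §9.6, training manual §1.b |
| Kit test | morning of the repellent test (days 1 to 3) | none | §§7.2, 9.1.2.7 |
| Efficacy test | days 1 to 3 | one treated forearm per product, ticks | §§7.2, 8.1, 10.3.6 |

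**Consequence by type of subject**

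- Dosimetry, then efficacy: tested at least 2 days, and up to about a month, after first product contact.
- Dosimetry only: never tested under the text shown.
- Efficacy only: tested before first repellent contact, but after tick training.

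**Applications before any test.** The dosimetry forms have one practice row and three sampling rows per arm, and the limb-dimensions paragraph within §10.3 defines limb as the forearm.

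- Per product: (1 + 3) × 2 arms = 8.
- A subject in all three products: 8 × 3 = 24.

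These count rows on the forms. Sampling alone gives 3 × 2 = 6 per product and 6 × 3 = 18 for three.

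**Places affected.** 10 subjects × 3 formulations = 30 dosimetry places. The overlap with efficacy testing is not fixed, so between 0 and 30 of these places may be held by people who do not continue. Zero requires every dosimetry subject to go on. §9.1.3 allows a single set of 10 people to do everything, but thinks it much more likely that substantially more will take part.

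**The case against.** The strongest reply is that known pregnancy is already screened. The exclusion is worded in terms of known status, and §9.1.5.3 has every candidate address each exclusion criterion in a private interview before any exposure. This stands. A reader might infer that nothing enforces the exclusion before first exposure, and the documents do not support that. What comes late is the layer that detects an unrecognised or unreported pregnancy.

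The second reply is that dosimetry exposure is slight. §5.4 says the repeat exposures are brief and washed off, with total time much shorter than one consumer application, and §10.2 has dosimeters weighed one to five minutes after application. This also stands. The count of 8 or 24 is a count of applications and does not show that dosimetry gives more exposure than an efficacy application worn for hours. But §5.4 does not exempt dosimetry from the eligibility rule.

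Other stronger readings also fail:

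- **Every efficacy subject has met product before the test.** Efficacy-only subjects have not.
- **Applications could reach 16 per product, or 48 in all.** That needs the leg fields of the forms. This protocol defines limb as the forearm, and the pump-spray manual carries the reference of the companion study SPC-001.
- **About 14 women are affected.** Applying the volunteer database's 28 women among 58 people to 30 places gives 30 × 28/58 = 14.5 places, not persons, and assumes enrolment mirrors the database. One set of 10 people would give 10 × 28/58 = 4.8.
- **Tick training is an equal breach.** It uses no repellent, and the ticks are described as disease-free. Whether the gate should cover it is a question for the sponsor.

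Lastly, the consent form was not among the pages available for this review and could carry further wording. The eligibility, screening and alternates sections nevertheless all give the test day.

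**Conclusion.** The point holds for dosimetry. Followed as written, the protocol lets a woman with an unrecognised or unreported pregnancy apply test material to her forearms up to 8 times per product, and 24 times across three products, before the protocol's own test. A dosimetry-only subject is never tested.

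The conclusion depends on the order of the phases and on the possibility of dosimetry-only subjects, both of which the text states. It does not depend on the application counts or on any assumed share of women. It does assume that the unseen consent pages add no earlier test.

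This is a subject-safety consistency correction. It does not touch complete protection time, its estimation or the sample size. It should be settled before dosimetry begins, because a later correction cannot reach subjects who have already finished that phase.

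**What to change.** Reconcile §§9.1.2.7, 9.1.5.3 and 9.1.7 with §§5.2, 7.2, 8.1 and 10.2, so that the existing kit check and technician verification come before a subject's first contact with test material in whichever phase that occurs, dosimetry included. Extend the §9.1.7 arrangement to the dosimetry session. As written it protects privacy only on the day of testing, so a positive result at dosimetry would have no such cover. The sponsor should also state whether tick training under §9.6 falls under the same gate, and align the consent wording.

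The cost is a few more over-the-counter kits, one more self-test for female dosimetry subjects, and edits to the three sections that give the timing. No endpoint or analysis changes.

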The U.S. EPA has historically required a minimum of six subjects. Given that test repellents are nearly certain to exhibit greater than zero efficacy, and that testing is conducted under adequate ambient tick questing pressure, it is nearly certain that no untreated limbs will register fewer or later crossings than any treated limbs. Six is often regarded as a statistically sufficient sample for an observation set because the increment in the confidence of means estimate begins to drop off sharply at that point. Notably, under the historical guidelines, there seem to have been few problems with EPA registering repellents that commonly fail to meet their labeled performance specification.

The main scientific risk of using a very small sample, however, is that the probability of over-representing subjects inherently unattractive to ticks is rather large, as is the risk of substantial biasing from a single subject that generates unrepresentative values for undetected reasons. The fact that the study will not be replicated for registration purposes increases that risk substantially. Note that in our interpretation of the draft EPA guidelines, the response variable, Time to First Confirmed Crossing, is calculated as the average duration for all treated subjects. There is no consideration of variation. In any given study, increasing the number of treated subjects to 10 will improve the probability of accurately estimating the population mean.

The 95% confidence interval computation is useful for assessing the certainty of a means estimate, and for normal probability density function that interval is ± 1.96 standard error of the mean. In this study we anticipate that the distribution of Times to First Confirmed Crossings will be truncated toward the origin. Because available mean and variance data on

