Picaridin efficacy (e.g., Carroll¹) indicates that no individual values will be near zero, approximating the exponential model with the normal model is likely justifiable. Using the rule of thumb that a distribution in which the mean is greater than three standard deviations above zero may be regarded as effectively normal, it is sensible to compute and report the normal 95% confidence interval in this study. Alternatively, if tests indicate substantial deviation from a normal distribution, the deviation will be corrected prior to analysis. An exception would be cases in which there is frequent truncation of records ('data censoring') due to subject withdrawals before product failure. In that case, other means of analysis (Kaplan-Meier survival analysis, §11.3.1) will be employed, but that possibility is not strongly related to sample size considerations.

To consider an example, in a study of repellency employing 8 subjects, Cilek et al.² recorded a mean protection time of approximately 180 minutes, with a standard error of about 15 minutes. Had the N been 6, we can roughly predict that the 95% CI would be 148-212. At $N=10$, the estimate would be 155-205. At $N=20$, the interval would be roughly 162-198. Evidently, adding the additional 10 subjects to reach an N of 20 shrinks the interval, in absolute terms, no more than did the addition of 4 subjects to increase the sample size from 6 to 10.

To summarize, in the case of a highly efficacious repellent, adding subjects beyond 6 is likely to increase the precision of the means estimate only slowly. However, the regulatory justification for this study is predicated on an aversion to assuming that efficacy is closely predictable in new formulations. That conservatism is further justified on the basis of the individual and public health importance of

¹ Carroll, S. P. (2006) Evaluation of topical insect repellents and factors that affect their performance. Chapter 12 in *Insect Repellents: Principles, Methods, and Use*, Debboun, M., Strickman, D. and Frances, S. P. (eds.). Boca Raton, Florida, CRC Press.

² Cilek, J. E., Peterson J. L. and Hallmon, C. F. (2004). Comparative efficacy of IR3535 and DEET as repellents against adult *Aedes aegypti* and *Culex quinquefasciatus*. *J. Amer. Mosq. Control Assoc.* 20: 299-304

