Subject effects on dosing behavior will be examined with nonparametric tests for n - sample independent cases (Kruskal-Wallis tests). In multiple regression analysis, the average amount of test material intercepted by each subject's dosimeters, as well as dosing per unit of skin surface area, will be examined in relation to the distance from nozzle to skin, limb size and the number of times the pump was actuated. The relationship between dosing behavior and dosage will also be examined with Spearman-rank correlation tests.

11.3.2. Repellency:

Because all subjects use different ticks, all ticks are used only once, and neither organism interacts directly with conspecifics at the level of the skin and the repellent during data collection, we will analyze data by subject as independent, replicated values. The hypothesis that the test materials will significantly reduce the number of ticks Crossing treated versus untreated skin is *not* the focus of this study. The focus is to compute, for each test material, a reasonable estimate of mean and standard deviation for the duration between application and sufficient repellency breakdown such that two ticks crossing on a subject within a half hour period. That pattern is here assessed at a resolution of 15 minutes.

Complete protection time (CPT) is measured as the length of time from initial application to the First Confirmed Crossing. A FCC is a Crossing followed by another Crossing within 30 minutes. For example, a Crossing at 90 minutes followed by another at 135 minutes is not confirmed, but a third Crossing at 150 minutes would confirm that at 135 minutes, giving a CPT of 135 minutes.

CPT measured in this way will yield a single time value for each subject. Mean CPT will be calculated across all 10 subjects per treatment, and will be presented with standard deviation and 95% confidence interval information as well.

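### Section 9.1.3 builds the 95% CI for mean CPT with the normal multiplier 1.96, although the SD is estimated from 10 subjects; followed as written, the interval covers about 92% and is about 13% too narrow

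*Protocol*

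**What the plan says.** Section 9.1.3 (Number of Subjects and Rationale for Sample Sizes) introduces the confidence interval as a measure of how certain an estimated mean is, and gives its form: "for normal probability density function that interval is ± 1.96 standard error of the mean". After arguing that CPT values should be close enough to normal, it concludes that "it is sensible to compute and report the normal 95% confidence interval in this study".

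The same section sets the sample size ("In both dosimetry and efficacy testing, we will engage 10 subjects per treatment") and concedes that little is known in advance: "In the absence of clear means of estimating the distribution of outcome values, it is difficult to predict an ideal sample size". It illustrates precision with a published repellent study of 8 subjects, mean about 180 minutes and standard error about 15 minutes. From this it derives "Had the N been 6, we can roughly predict that the 95% CI would be 148-212", then 155-205 at N = 10 and about 162-198 at N = 20.

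Section 11.3.2 (Repellency) makes the interval part of the planned results: "Mean CPT will be calculated across all 10 subjects per treatment, and will be presented with standard deviation and 95% confidence interval information as well". It does not say how the interval is formed. No section mentions a t quantile.

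**The concern.** The multiplier 1.96 is right when the standard error is known. Here it is computed from the SD of the same 10 subjects, and its sampling error has to be allowed for. The protocol defends the normal interval by arguing that the data will be nearly normal, but that does not settle the matter: with perfectly normal data and an estimated SD, the exact interval uses Student's t on n−1 degrees of freedom.

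Mean CPT with its SD and 95% interval is the planned summary for each of the three test materials, and section 5.2 says the study's information will serve as a basis for labeling. An interval called 95% that covers less overstates certainty. The example used to discuss sample size would carry the same error.

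**Working it through.** **Inputs.** n = 10 per treatment (9.1.3, 11.3.2); multiplier 1.96 (9.1.3); SD estimated from the sample (11.3.2); example mean about 180 min and SE about 15 min at n = 8 (9.1.3). The implied SD is 15 × √8 = 42.4 min.

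**1. Reproduce the stated example.** Half-width = 1.96 × SD/√N.

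| N | Stated | z, SD 42.4 | z, SD 40 |
|---|---|---|---|
| 6 | 148-212 | 146-214 | 148-212 |
| 10 | 155-205 | 154-206 | 155-205 |
| 20 | 162-198 | 161-199 | 162.5-197.5 |

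With SD 42.4, every limit is within 2 minutes of the stated one; with SD 40, the match is nearly exact.

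**2. Which multiplier was used?** Solve the stated half-widths (32, 25, 18) for the SD.

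- With z, SD = half-width × √N / 1.96 = 40.0, 40.3 and 41.1, which is essentially one value.
- With t (2.571, 2.262, 2.093), SD = 30.5, 34.9 and 38.5. No single SD gives all three intervals.

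The example therefore used 1.96.

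**3. Coverage of mean ± 1.96 × SD/√n with estimated SD.** Under normality this is P(|t with n−1 df| < 1.96):

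- n = 6: 89.3%
- n = 10: 91.8%
- n = 20: 93.5%

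**4. Width at n = 10.** 2.262/1.96 = 1.154, so the t interval is 15.4% wider. Equivalently, 1.96/2.262 = 0.866, so the z interval is about 13% too narrow.

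**5. Sensitivity to shape and to the 15-minute grid.** Simulation with n = 10, mean 180 and 200,000 runs per case. The CV of 0.236 is 42.4/180; the CV of 0.333 is the limit of the protocol's own rule that the mean exceed three SDs.

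| CPT distribution | z coverage | t coverage |
|---|---|---|
| Normal, rounded up to 15 min | 91.9% | 95.1% |
| Gamma, CV 0.236 | 91.6% | 94.7% |
| Gamma, CV 0.333 | 91.3% | 94.4% |

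The t interval stays close to 95% in these cases and the z interval does not.

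**6. The example with t.** Half-width = t(0.975, N−1) × SD/√N.

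| N | Stated | t, SD 42.4 | t, SD 40 |
|---|---|---|---|
| 6 | 148-212 (width 64) | 135-225 (89) | 138-222 (84) |
| 10 | 155-205 (50) | 150-210 (61) | 151-209 (57) |
| 20 | 162-198 (36) | 160-200 (40) | 161-199 (37) |

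**7. Effect on the sample-size argument.** The stated widths fall by 64 − 50 = 14 min from N = 6 to 10, and by 50 − 36 = 14 min from 10 to 20. With t and SD 42.4 the falls are 89 − 61 = 28 and 61 − 40 = 21 min. The step from 6 to 10 is worth more than the protocol shows, and its remark that going on to 20 gains no more than going from 6 to 10 still holds.

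**The case against.** The strongest reply is that the protocol does not bind the analyst to 1.96. The sentence with that figure is a general statement in a sample-size discussion and is correct for a known standard error. The word normal can be read as choosing a normal over an exponential model, not z over t. Section 11.3.2, which governs reporting, gives no multiplier, and 11.3 leaves computation to statistical software.

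Part of this stands. A reader might infer that every interval reported will cover only 92%. The documents do not support that unconditionally, because a t interval would be compatible with 11.3.2. The reading of normal as a matter of shape alone does not stand, however: 9.1.3 defines the interval by 1.96, says to report that normal interval in this study, and illustrates it with intervals that only z reproduces.

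A second reply concerns consequence. Section 11.3.2 plans no statistical comparisons; the mean, SD and n will be available, so anyone can form the t interval; Kaplan-Meier estimates are also planned. With the example's inputs at N = 10, the half-width moves from 26.3 to 30.4 min, about 4 min, against a 15-minute assessment grid. This stands, and it limits the importance of the point. It does not make the interval correct, and Kaplan-Meier medians do not repair an interval for the mean.

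The gap between an SD of 42.4 and the SD of about 40 behind the example might also look like an error. It is rounding: the source figures are given as approximate and the predictions as rough.

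**Conclusion.** Wrong as written, of moderate importance. If 9.1.3 is followed, the nominal 95% interval for mean CPT at n = 10 covers about 91.8%, and is about 13% narrower than it should be. This assumes independent, approximately normal CPT values, an SD estimated from the 10 subjects, and no censoring. The size barely changes for the 15-minute grid or moderate right skew. The example intervals are too narrow at every N, most of all at N = 6 (width 64 stated, 84 to 89 with t).

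Two stronger conclusions are not supported. One is that the sample size is undermined: the t-based figures strengthen the case for 10 over 6, and 9.1.3 also rests that choice on limiting the influence of any one subject. The other is that a label claim or regulatory decision turns on this interval: section 5.2 links the study's information to labeling, but no section makes a confidence limit the input, and no test or margin uses it.

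**What to change.** In 9.1.3 and 11.3.2, specify the interval as mean ± t(0.975, n−1) × SD/√n, with 2.262 for 10 subjects, so that the two sections agree. In 9.1.3, restate the example as approximately 135-225 (N = 6), 150-210 (N = 10) and 160-200 (N = 20) using SD 42.4, or 138-222, 151-209 and 161-199 using SD 40, and say which SD is used.

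The change is wording only. Design, number of subjects and data collection stay as they are. Relative to following 9.1.3 as written, the reported intervals at n = 10 become about 15% wider.
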